**Protocol No./Title:** A Multi-Center, Randomized, Double-Masked, Vehicle-Controlled, Parallel-Group, Study to Evaluate the Safety and Efficacy of CSB-001 Ophthalmic Solution 0.1% in Stage 2 and 3 Neurotrophic Keratitis Subjects

**NCT No.:** 04909450

**Document Date:** 21 July 2023

8. Dispense test article according to assigned kit number using IBM CD
  - Dispense one new unopened kit; this kit is considered the back-up kit. The back-up kit dispensed at the last visit is now considered the primary kit. Instruct subject to use the remaining test articles that were dispensed at the last visit prior to opening and using the kit dispensed at this visit.
  - Remind subject regarding test article storage and administration.
  - Instruct subject that all test articles will need to be stored in the refrigerator (2-8 deg C) (or in cooler bag if away from home) until time of administration. Test article must be protected from light; instruct subject to keep vials in the pouch until the time of administration.
  - Instruct subject to keep used BFS vials and to bring to the next visit along with the subject diary
9. Schedule the subject for the next follow-up study visit (Week 3 Visit)
  - Instruct subject to bring all used and unused test articles from the opened primary kit to the visit.
  - If the back-up kit was used, instruct the subject to also bring used and unused test articles from the opened back-up kit to the visit. Unopened and unused back-up kits will be kept refrigerated at the subject's residence.

#### **6.1.4. Week 3 Visit ( $\pm 2$ day window)**

Note: Perform ophthalmic assessments in the study eye only

1. Record any changes in medical history and concomitant medications/therapies
2. Record any adverse events since the last visit
3. Assess test article compliance (including collection of used BFS vials, accountability of test articles, and review of subject diary)
4. Perform logMAR pinhole distance VA
5. Perform slit-lamp exam (without fluorescein staining)
6. Perform digital imaging of the corneal fluorescein staining
  - Two sets of images will be captured at each timepoint where digital imaging is required. The first set of images will be collected  $30 \pm 15$  seconds after fluorescein instillation. The second set of images will be collected  $120 \pm 15$  seconds after fluorescein instillation.
7. Perform investigator assessment of corneal healing and NEI scale assessment of corneal staining (additional fluorescein may be instilled per investigator discretion)
8. Dispense test article according to assigned kit number using IBM CD
  - Dispense one new unopened kit; this kit is considered the back-up kit. The back-up kit dispensed at the last visit is now considered the primary kit. Instruct subject to use

the remaining test articles that were dispensed at the last visit prior to opening and using the kit dispensed at this visit.

- Assess the inventory for the back-up kit and dispense another back-up kit as needed. In the event that additional vials are needed to complete dosing until the next follow-up visit, the back-up kit will be used.
- Remind subject regarding test article storage and administration
- Instruct subject that all test articles will need to be stored in the refrigerator (2-8 deg C) (or in cooler bag if away from home) until time of administration. Test article must be protected from light; instruct subject to keep vials in the pouch until the time of administration.
- Instruct subject to keep used BFS vials and to bring to the next visit along with the subject diary

9. Schedule the subject for the next follow-up study visit (Week 4 Visit)

- Instruct subject to bring all used and unused test articles from the opened primary kit to the visit.
- If the back-up kit was used, instruct the subject to also bring used and unused test articles from the opened back-up kit to the visit. Unopened and unused back-up kits will be kept refrigerated at the subject's residence.

**6.1.5. Week 4 Visit ( $\pm 2$  day window)**

Notes:

- Perform ophthalmic assessments in the study eye only.
  - This visit should be scheduled to coincide with one of the times for test article administration. Instruct subject to refrain from dosing until they are at the office to allow for assessment of ocular tolerability.
1. Record any changes in medical history and concomitant medications/therapies
  2. Record any adverse events since the last visit
  3. Assess test article compliance (including collection of used BFS vials, accountability of test articles, and review of subject diary)
  4. Administer the ocular tolerability questionnaire immediately after in-office administration of the test article
  5. Perform logMAR pinhole distance VA
  6. Perform slit-lamp exam (without fluorescein staining)
  7. Perform digital imaging of the corneal fluorescein staining
    - Two sets of images will be captured at each timepoint where digital imaging is required. The first set of images will be collected  $30 \pm 15$  seconds after fluorescein instillation. The second set of images will be collected  $120 \pm 15$  seconds after fluorescein instillation.

8. Perform anterior segment OCT (only at selected sites)
9. Perform investigator assessment of corneal healing and NEI scale assessment of corneal staining (additional fluorescein may be instilled per investigator discretion)
10. Dispense test article according to assigned kit number using IBM CD
  - Dispense one new unopened kit; this kit is considered the back-up kit. The back-up kit dispensed at the last visit is now considered the primary kit. Instruct subject to use the remaining test articles that were dispensed at the last visit prior to opening and using the kit dispensed at this visit.
  - Assess the inventory for the back-up kit and dispense another back-up kit as needed. In the event that additional vials are needed to complete dosing until the next follow-up visit, the back-up kit will be used.
  - Remind subject regarding test article storage and administration
  - Instruct subject that all test articles will need to be stored in the refrigerator (2-8 deg C) (or in cooler bag if away from home) until time of administration. Test article must be protected from light; instruct subject to keep vials in the pouch until the time of administration.
  - Subjects will be instructed to keep used BFS vials and to bring to the next visit along with the subject diary
11. Schedule the subject for the next follow-up study visit (Week 5 Visit)
  - Instruct subject to bring all used and unused test articles from the opened primary kit to the visit.
  - If the back-up kit was used, instruct the subject to also bring used and unused test articles from the opened back-up kit to the visit. Unopened and unused back-up kits will be kept refrigerated at the subject's residence.

**6.1.6. Week 5 Visit ( $\pm 2$  day window)**

Note: This is a drug dispensation visit; no ophthalmic assessments are required.

1. Assess test article compliance (including collection of used BFS vials, accountability of test articles, and review of subject diary)
2. Dispense test article according to assigned kit number using IBM CD
  - Dispense one new unopened kit; this kit is considered the back-up kit. The back-up kit dispensed at the last visit is now considered the primary kit. Instruct subject to use the remaining test articles that were dispensed at the last visit prior to opening and using the kit dispensed at this visit.
  - Assess the inventory for the back-up kit and dispense another back-up kit as needed. In the event that additional vials are needed to complete dosing until the next follow-up visit, the back-up kit will be used.
  - Remind subject regarding test article storage and administration

- Instruct subject that all test articles will need to be stored in the refrigerator (2-8 deg C) (or in cooler bag if away from home) until time of administration. Test article must be protected from light; instruct subject to keep vials in the pouch until the time of administration.
  - Subjects will be instructed to keep used BFS vials and to bring to the next visit along with the subject diary
3. Schedule the subject for the next follow-up study visit (Week 6 Visit)
- Instruct subject to bring all used and unused test articles from the opened primary kit to the visit.
  - If the back-up kit was used, instruct the subject to also bring used and unused test articles from the opened back-up kit to the visit. Unopened and unused back-up kits will be kept refrigerated at the subject's residence.

**6.1.7. Week 6 Visit (±2 day window)**

Refer to the Week 2 Visit (Section 6.1.3). The same procedures are performed except schedule the subject for the next follow-up study visit (Week 7 Visit).

**6.1.8. Week 7 Visit (±2 day window)**

Refer to the Week 5 Visit (Section 6.1.6). The same procedures are performed except schedule the subject for the next follow-up study visit (Week 8 Visit).

**6.1.9. Week 8 Visit (±2 day window)**

Notes:

- It is critical that all subjects return for the Week 8 Visit to ensure an adequate number of evaluable subjects for analysis. Site personnel will apply due diligence to contact the subject to return for the Week 8 Visit.
  - This visit should be scheduled to coincide with one of the times for test article administration. Instruct subject to refrain from dosing until they are at the office to allow for assessment of ocular tolerability.
  - Depending on the time of the Week 8 Visit, the subject may not be able to dose with all four doses for the day. The subject's last dose should take place in the office in order to assess ocular tolerability. Dosing will be discontinued prior to the conduct of the ophthalmic study assessments at the Week 8 Visit.
1. Collect all test articles (used and unused)
  2. Record any changes in medical history and concomitant medications/therapies
  3. Record any adverse events since the last visit
  4. Assess test article compliance (including collection of used BFS vials, accountability of test articles, and review of subject diary)

5. Administer the ocular tolerability questionnaire immediately after in-office administration of test article
6. Perform logMAR pinhole distance VA OU
7. Perform slit-lamp exam OU (without fluorescein staining)
8. Perform digital imaging of the corneal fluorescein staining in the study eye
  - Two sets of images will be captured at each timepoint where digital imaging is required. The first set of images will be collected  $30 \pm 15$  seconds after fluorescein instillation. The second set of images will be collected  $120 \pm 15$  seconds after fluorescein instillation.
9. Perform anterior segment OCT in the study eye (only at selected sites)
10. Perform investigator assessment of corneal healing and NEI scale assessment of corneal staining (additional fluorescein may be instilled per investigator discretion)
11. Assess corneal sensitivity using the Cochet-Bonnet aesthesiometer on the study eye (at select sites with a Cochet-Bonnet)
12. Perform Schirmer's test without anesthesia in the study eye
13. Perform IOP OU
14. Perform dilated ophthalmoscopy OU
15. Perform urine pregnancy test if the subject is a female of childbearing potential
16. Based on the investigator assessment of corneal healing, proceed as described below:
  - Subjects with corneal healing at Week 8 as assessed by the investigator will return at Week 10 for assessment of sustained healing. Schedule the subject for the next follow-up study visit (Week 10 Visit).
  - Subjects with incomplete corneal healing at Week 8 as assessed by the investigator will be unmasked. Sites will be provided instructions to unmask the subject using the IMB CD system.
    - Subjects randomized to vehicle will be eligible per investigator discretion to enter the uncontrolled treatment phase and receive 8-week treatment with CSB-001. See Section 6.2.
    - Subjects randomized to CSB-001 will exit the study and be treated per investigator discretion. See Section 6.3 for the study procedures required to be completed at the time of study exit.

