### **7.13. Digital Imaging of Corneal Fluorescein Staining**

Digital imaging of corneal fluorescein staining will be performed prior to any procedures that touches the eye and prior to instillation of any topical agents except for fluorescein.

This procedure will be performed using a slit-lamp equipped with a camera after instillation of fluorescein (using a fluorescein strip and non-preserved saline) into the lower palpebral conjunctiva. Two sets of images will be captured at each timepoint where digital imaging is required per the Schedule of Events. **The first set of images will be collected  $30 \pm 15$  seconds after fluorescein instillation. The second set of images will be collected  $120 \pm 15$  seconds after fluorescein instillation.** Capturing the photos at the specified times is critical to ensure appropriate staining of the NK lesion. Additional images may be captured to ensure quality images are obtained.

Images will be uploaded electronically to a portal for assessment by masked readers at the study designated central reading center (CRC). Certification of the equipment and examiners at each investigative site will occur prior to evaluation of study subjects. Refer to the reading center manual for additional information.

In the event that fluorescein was instilled for another procedure on the same day prior to digital imaging, wait at least 2 hours before re-instilling fluorescein, then perform imaging.

[figure not shown]

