## 17. APPENDICES

**Table 2: Schedule of Assessments**

Randomized, Double-Masked, Controlled Treatment Phase (8-week dosing; 1:1 randomization to CSB-001 or vehicle)												
Study Procedures	Screening/Randomization (Baseline Visit)	Day 0 	Wk 1	Wk 2	Wk 3	Wk 4	Wk 5	Wk 6	Wk 7	Wk 8 	Wk 10 	Early Exit 
Informed Consent		X										
Inclusion/Exclusion Criteria		X										
Demographics and Medical History (Systemic and Ocular)		X										
Previous/Change in Concomitant Meds (Systemic and Ocular)		X	X	X	X	X		X		X	X	X
Adverse Events Query		X 	X	X	X	X		X		X	X	X
Test Article Compliance			X	X	X	X		X		X		X
Ocular Tolerability Questionnaire 		X				X				X		
LogMAR Pinhole Distance VA		OU	SE 	SE	SE	SE		SE		OU	SE	OU
Slit-Lamp Examination		OU	SE 	SE	SE	SE		SE		OU	SE	OU
Digital Imaging of Corneal Fluorescein Staining		SE	SE	SE	SE	SE		SE		SE	SE	
Investigator Assessment of Corneal Healing			SE	SE	SE	SE		SE		SE	SE	
NEI Scale Assessment		SE	SE	SE	SE	SE		SE		SE	SE	
Corneal Sensitivity 		SE								SE		
Schirmer's Test (Non-Anesthetized)		SE								SE		
Anterior Segment OCT (at selected sites)		SE				SE				SE		
Intraocular Pressure (IOP)		OU								OU		OU
Dilated Fundus Ophthalmoscopy		OU								OU		OU
Urine Pregnancy Test (Female of Childbearing Potential)		X								X		X
Randomization		X										
Study Drug Dispensation		X 	X	X	X	X	X	X	X			

Note: A ±2 day visit window is allowed for all scheduled visits except for the Week 10 Visit where the window is -2 to +7 days.

OU= both eyes, SE=study eye, VA=visual acuity

All procedures to be performed prior to first dose of test article except for adverse events and ocular tolerability assessments.

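### At Weeks 4 and 8 the visit lists put the in-office drop before fluorescein imaging and AS-OCT, although Protocol Sections 7.13 and 7.16 require both before any topical agent other than fluorescein

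*Protocol*

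**What the plan says.** Protocol Section 7.13 sets the rule for the images sent to the CRC: they are taken "prior to any procedures that touches the eye and prior to instillation of any topical agents except for fluorescein". Section 7.16 repeats the condition for AS-OCT at the selected sites.

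At Week 8 (Section 6.1.9) the subject holds the dose until the visit. The notes say "The subject's last dose should take place in the office in order to assess ocular tolerability" and then "Dosing will be discontinued prior to the conduct of the ophthalmic study assessments at the Week 8 Visit". The numbered list follows the notes. Step 5 is "Administer the ocular tolerability questionnaire immediately after in-office administration of test article", step 6 is "Perform logMAR pinhole distance VA OU", step 8 is "Perform digital imaging of the corneal fluorescein staining in the study eye", step 9 is AS-OCT and step 10 is the investigator's healing assessment.

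Week 4 (Section 6.1.5) also has the subject arrive undosed. Step 4 is "Administer the ocular tolerability questionnaire immediately after in-office administration of the test article", and VA, imaging, AS-OCT and the healing assessment follow.

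For Day 0, the first footnote of Table 2 says "All procedures to be performed prior to first dose of test article except for adverse events and ocular tolerability assessments". The Week 10 list (6.1.10) contains no test article. Sections 6.2.5 and 6.2.9 carry the Week 4 and Week 8 procedures into the uncontrolled phase by cross-reference.

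**The concern.** The test article is an ophthalmic solution instilled as a drop, so it is a topical agent within the meaning of 7.13. At two visits the list therefore requires what the imaging section rules out, and one of those visits supplies half of the primary endpoint.

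Three things are at stake.

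- **Comparability over time.** Complete healing needs a CRC reading of 0 mm at both Week 8 and Week 10 (Section 11.1). One image follows a drop and the other does not. The baseline image does not either.
- **Other results from the same visits.** CRC healing at Week 4 and at Week 8 are key secondary endpoints read from post-drop images. The time-to-event and lesion-size endpoints also draw on them. The investigator's healing call at Week 8, also made after the drop, decides who is unmasked and who returns at Week 10. For vehicle subjects who enter the uncontrolled phase at Week 8, the post-drop image becomes their baseline (6.2.1.1). For those who enter at Week 10 it is a drop-free image (6.2.1.2).
- **Uniform conduct.** With two conflicting instructions, sites have no single order to be trained on or monitored against.

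**Working it through.** No figure in the plan depends on this point, so the check compares the order of procedures. Step numbers come from Sections 6.1.5, 6.1.9 and 6.1.10. The Day 0 order comes from the Table 2 footnote, because the Day 0 visit section is not in the text available.

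| Visit | Test-article drop | VA | Fluorescein imaging | AS-OCT | Investigator healing call |
|---|---|---|---|---|---|
| Day 0 | after all of these | before drop | before drop | before drop | not scheduled |
| Week 4 | by step 4 | step 5 | step 7 | step 8 | step 9 |
| Week 8 | by step 5 | step 6 | step 8 | step 9 | step 10 |
| Week 10 | none | step 3 | step 5 | not scheduled | step 6 |

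1. *Against 7.13.* At Week 4 the drop comes before imaging (4 before 7), and at Week 8 likewise (5 before 8). Both conflict with the rule.
2. *Against 7.16.* At Week 4 the drop comes before AS-OCT (4 before 8), and at Week 8 likewise (5 before 9). Both conflict, at the selected sites.
3. *Is it a numbering slip?* Not at Week 8, where the notes state the order in words. At Week 4 it rests on the numbered list and the instruction to hold the dose until the visit.
4. *Is there an interval that would reconcile them?* None is given between the test-article drop and fluorescein. The only wait in 7.13, at least 2 hours, concerns fluorescein instilled earlier the same day.
5. *Against 7.7 (VA).* That section requires VA before contact examinations and dilation and does not mention topical agents. VA after the drop breaches nothing. It only differs from Day 0.
6. *Extent.* Table 2 schedules controlled-phase imaging at Day 0 and Weeks 1, 2, 3, 4, 6, 8 and 10, which is eight visits. Two of the eight, Weeks 4 and 8, follow an in-office drop, in both arms.
7. *Route to the primary endpoint.* An eye wrongly read as healed at Week 8 counts as a responder only if the CRC also reads 0 mm at Week 10, when no test article is given. If Week 10 is missing, the subject is a non-responder (13.3.1). The Week 10 image gives no such check on an eye wrongly read as unhealed at Week 8. The documents do not show that either error occurs.

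**The case against.** The strongest reply accepts the textual conflict but denies that it matters. The Week 8 note shows that dosing first was deliberate. Both arms receive a drop at the same step, CRC readers are masked, and VA and the slit-lamp examination fall between drop and imaging. Imaging itself adds saline with the fluorescein strip and takes two timed sets of images. The Manual of Procedures and the reading center manual, which are not available here, may say more. Reordering Weeks 4 and 8 would also not fully standardise conditions: 7.13 sets no interval since the last home dose, and the Week 3 list does not ask subjects to withhold one.

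Much of this stands, and it rules out three stronger readings.

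- A reader might infer that the drop washes out or dilutes stain and so inflates healing rates. The documents say nothing of the kind, and the drop is given before fluorescein is instilled.
- A reader might assume a misread rate and compute a loss of power. No such rate is given. The planning rates of 60% and 30% are for healing at both Week 8 and Week 10, not at Week 8 alone.
- A reader might infer bias between the arms. Nothing in the documents shows that the active and vehicle drops affect staining differently.

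The conflict itself survives. A deliberate order in 6.1.9 does not remove a contrary rule in 7.13, and no other section says which prevails. The protocol itself calls the timing of image capture critical to proper staining of the lesion, so the conditions just before capture should not rest on contradictory instructions.

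**Conclusion.** The contradiction is established from the protocol's own text: 6.1.5 and 6.1.9 against 7.13 and 7.16, repeated in the uncontrolled phase. As written, the Week 8 image for the primary endpoint is taken after a drop, and the Day 0 and Week 10 images are not.

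The reach is wide: every subject imaged at Week 4 or Week 8, in both arms. The size of any effect on staining is unknown and cannot be calculated from the documents. There is no evidence of a directional effect on the treatment comparison, and the Week 10 requirement limits what can pass into the primary endpoint. The Week 4 and Week 8 CRC endpoints are single-visit readings and lack that protection.

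This conclusion assumes that the Table 2 footnote describes the Day 0 order correctly and that no manual outside these documents already resolves the conflict. It does not extend to VA, where no rule is broken.

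**What to change.** Reconcile 6.1.5 and 6.1.9 with 7.13 and 7.16 so that one stated order applies at every site. The order that meets 7.13 and 7.16 and matches Day 0 and Week 10 is to complete digital imaging, AS-OCT and the investigator healing assessment first, and then give the in-office drop and questionnaire. The Week 8 note on when dosing stops would need rewording to agree. Placing the questionnaire ahead of the IOP, dilation and unmasking steps keeps it clear of anaesthetic and dilating drops and of knowledge of treatment. VA can be moved ahead of the drop at the same time, for comparability with Day 0 only. The dosing regimen is not in question.

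If the sponsor prefers to keep the drop first, 7.13 and 7.16 need an explicit exception and a stated interval between drop and fluorescein. The images would then still differ in condition from Day 0 and Week 10.

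The cost is an edit to existing steps in two visit sections, with matching changes to the Manual of Procedures and reading center manual if they repeat the order. The uncontrolled-phase visits follow by cross-reference. The drawback is that tolerability is then recorded after fluorescein. The edit does not control the time since the last home dose at the other imaging visits.
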